#### Part 2: Monitor more closely the course of respiratory function over time in patients with ALS by using remote pulmonary function testing, performed via telemedicine.

*Primary Hypothesis:* Home respiratory assessment enables thresholds for Non-invasive ventilation (NIV) recommendation to be met in the experimental group significantly closer to the initiation criteria, at a time when quality of life is higher, compared to the control group.

*Secondary Hypothesis:* Telemonitoring of respiratory health in the experimental group will maintain higher quality of life, and lengthen survival.

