- 3) Short Form 36 (SF-36) [Ware1992]. This is a generic, coherent, and easily administered quality-of-life measures which has been shown to be sensitive for mental and physical health assessment in ALS [Bourke2006, Jackson2001, Bourke2003].
- 4) SAQLI parts E and F (NIV users only). These sections ask about problems that may have arisen due to NIV use and how respiratory symptoms may have been alleviated due to treatment during this period.

Each session concludes with recommendations from the therapist based on the results of respiratory tests. These can include behavioral modifications or recommendation for NIV. Recommendation of NIV is based on a measured FVC  $\leq$ 50% predicted or for dyspnea accompanied by MIP  $>$  -60 cm H2O. This recommendation will be reviewed by the ALS clinic neurologist. If the decision is made to initiate NIV, the ALS clinic physician will provide an order, and the ALS clinic nurse will arrange for initiation of in-home NIV via a third-party vendor according to usual standards of care.

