### **8.2 Sample size determination**

Our sample size is predetermined based on our subjective ability to recruit patients within the time frame of the study. Power analysis was based on studies of FVC decline. Lo Coco et al., [LoCoco2006], showed that 50% of study participants dropped below 50% predicted FVC in one year. Given that our exclusion criteria for Part 2 will reject many of the 37% of individuals in their study who were "slow progressors," we estimate that 75% of patients enrolled in our study will meet the respiratory criteria to recommend NIV. This results in a sample size per arm of n=15, which provides 80% power to detect a difference in mean outcome between the two groups if the effect size is found to be 0.95.

Assuming a monthly change in FVC of  $3.5 \pm 3.4\%$  found by Schiffman et al. [Schiffman1993], we conducted 10,000 Monte-Carlo simulations of 40 participants declining at this rate for 12 months. Half were sampled once every three months, and half were sampled every month.  $80.6 \pm 6.3\%$  of simulated participants met the requirements for NIV recommendation, in roughly equal proportions across groups. The average FVC at recommendation was 47.0% predicted in the experimental group, and 43.4% predicted in the control group. The effect size of the difference in FVC between groups was  $.964 \pm .343$ . Similarly, the two measures of QoL obtained at NIV recommendation are powered with an 80% chance to detect improvement of quality of life in the experimental group if the effect size is also found to be 0.95. This corresponds to a mean score difference of 1.52 on the SAQLI, assuming a standard deviation of 1.6 [Flemons1998]. Although there is no published data on the standard deviation of MDRS-D scores, the range and format of questions is similar enough to estimate a comparable difference between groups is needed.

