### **8.3 Statistical methods**

Part 1: The primary hypothesis is that there is no difference in the results of PFT and rPFT for respiratory assessment of FVC and MIP. We will use a paired sample t-test to determine if the mean test results are comparable between the standard and experimental treatments. We will conduct a qualitative analysis to determine whether the patient, caregiver, and therapist determine the rPFT to be an effective way to conduct tests of breathing function.

Part 2: The primary outcomes will be analyzed to determine if respiratory parameters are closer to the actionable threshold at NIV recommendation and whether QoL is better sustained at this point in individuals in the experimental group. This will be done using a non-parametric two sample test of means, the Wilcoxon-Mann-Whitney rank sum test.

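### Section 8.3 reads the Part 2 primary outcomes at a recommendation made by therapists who know the arm; earlier recommendation in the experimental arm would inflate the difference, so the index visit should be derived from recorded values

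*Combined protocol and SAP*

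**What the plan says.** Section 8.3 sets the reading point for both kinds of Part 2 primary outcome. The respiratory question is whether "respiratory parameters are closer to the actionable threshold at NIV recommendation", and the quality-of-life question is "whether QoL is better sustained at this point in individuals in the experimental group". Section 8.2 uses the same point for its quality-of-life power statement: "the two measures of QoL obtained at NIV recommendation are powered with an 80% chance".

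Section 7.2.2 says who acts: "Each session concludes with recommendations from the therapist based on the results of respiratory tests". It then ties the act to criteria. "Recommendation of NIV is based on a measured FVC" at or below 50% predicted, or on dyspnea together with MIP > -60 cm H2O, and the clinic neurologist reviews the recommendation.

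The hypothesis in Section 1.1 is worded differently. It expects "thresholds for Non-invasive ventilation (NIV) recommendation to be met in the experimental group significantly closer to the initiation criteria", which describes criteria being met rather than a recommendation being issued.

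The home tests, conducted by the therapist, exist only in the experimental arm (Section 7.2.2). No blinding of the therapist or the reviewing neurologist is described.

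**The concern.** The date on which the outcome is read is set by someone who delivers the intervention and knows the allocation. Both FVC and quality of life are expected to fall over time, so an earlier reading gives a better value. A slightly earlier recommendation for experimental patients would therefore move the result in the direction of the hypothesis.

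The opportunity is also unequal. After baseline, experimental patients have 4 clinic visits + 8 home tests = 12 sessions, and controls have 4.

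The plan does not say that a recommendation must issue at the first crossing, that it may not precede it, or which visit counts when the two differ. Section 13.0 has the therapist and nurse clinician follow up with the neurologist about NIV recommendation, so it is also unclear whose act, on which date, fixes the index visit.

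**Working it through.** **1. Where judgement can enter.**

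- *FVC route.* The criterion is numeric. If it is followed, a recommendation cannot precede the recorded crossing, so an early one would be a departure from Section 7.2.2.
- *Dyspnea with MIP route.* Dyspnea has no cut-off, no instrument and no named assessor. FVC may still be above 50% when this route is used.
- *The MIP criterion itself.* Sections 2.1 and 3.2 state MIP > -60 cm H2O without dyspnea, whereas Section 7.2.2 requires dyspnea as well. The trigger cannot be programmed until these are reconciled.
- *Validity of maneuvers.* Section 7.1 has remote testing repeated until the therapist is satisfied.

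**2. Reproducing the plan's own figure.** Inputs from Section 8.2: 40 patients, half tested monthly and half quarterly for 12 months, monthly decline 3.5 ± 3.4. Baseline FVC is not stated, so a fixed 82% is assumed. Each month's drop is an independent Normal(3.5, 3.4) draw, and the index is the first scheduled visit with FVC at or below 50%.

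| | Section 8.2 | Rebuilt |
|---|---|---|
| Met criteria | 80.6 ± 6.3% | 81.0 ± 6.2% |
| FVC at index, experimental vs control | 47.0 vs 43.4 | 47.0 vs 43.5 |
| Effect size | 0.964 ± 0.343 | 0.955 ± 0.345 |

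A baseline of Normal(75, 15) truncated above 50 gives nearly the same (47.0 vs 43.3, effect size 0.998). The plan's simulation therefore behaves as a pure first-crossing rule, with no discretion.

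**3. Adding early recommendation under the planned schedules.** A share of experimental patients is indexed one session before crossing, and no controls are. The shares are assumptions. The test is the two-sided rank-sum at 0.05; Section 8.3 states neither alpha nor sidedness.

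| Share moved early | Difference, any patient can move | Significant | Difference, only patients at ≤52% can move | Significant |
|---|---|---|---|---|
| 0% | 3.58 | 64% | 3.58 | 64% |
| 10% | 4.19 | 74% | 3.7 | 69% |
| 20% | 4.78 | 84% | 3.9 | 74% |
| 30% | 5.41 | 91% | 4.1 | 78% |

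Hand check of the any-patient column: the visit before crossing averages 53.3% and the crossing visit 47.0%, so each moved patient gains 53.3 − 47.0 = 6.3 points. Then 3.58 + 0.10 × 6.3 = 4.21, 3.58 + 0.20 × 6.3 = 4.84 and 3.58 + 0.30 × 6.3 = 5.47, close to the simulated values.

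In the right-hand columns the share applies only to patients whose preceding visit was at 52% or below. At that visit 63% are above 52, so 37% are eligible, and a 30% share moves about 0.30 × 37% = 11% of all crossers.

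**4. Separating discretion from the schedule.** With both arms tested monthly and no true difference, about 2.5% of trials are significant in favor of the experimental arm when nobody moves. With 10, 20 and 30% moved early, this becomes about 6, 16 and 30% if any patient can move, and 4, 6 and 9% if only patients at 52% or below can. Repeat runs of these simulations differ by a point or two.

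**5. Quality of life.** The documents give no relation between FVC and SAQLI or MDRS-D, so this part of the inflation cannot be sized.

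**The case against.** The strongest reply is that recommendation and criteria met are the same thing in this protocol. Section 7.2.2 ties the recommendation to measured values under neurologist review, Section 1.1 speaks of thresholds being met, and the Section 8.2 simulation is a first-crossing rule. Much of this stands. A reader might infer that the index is a free clinical opinion detached from the readings, and the documents do not support that. What does not stand is that nothing need be said: dyspnea is undefined, the review is not described as blinded and follows a recommendation already made, and no rule covers disagreement.

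A reader might also infer that therapist discretion could by itself create the trial's result. The figures do not show that. Under the planned schedules the difference is already about 3.6 points, and 64% of trials are significant, with no discretion at all. The rise to 91% is inflation on top of that, and it assumes that patients well above the threshold are moved as readily as those near it.

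Finally, no passage says that the therapist is the one who judges dyspnea. Patients rate their own breathlessness on the MDRS-D, and up to three therapists may take part (Section 8.1).

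**Conclusion.** The point holds in a limited form. The Part 2 primary outcomes are read at a decision made by people who know the arm, and that decision is open to judgement through the undefined dyspnea element or through departures from the FVC rule. Earlier recommendation in the experimental arm would inflate the FVC difference from about 3.6 points to 4.2–5.4 if any patient can move, or to 3.7–4.1 if only patients at 52% or below can.

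These sizes rest on assumed shares of 10–30%, no early recommendation among controls, an assumed 82% baseline and the plan's own decline model. The documents do not show that early recommendation will occur.

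It would be wrong to conclude that a programmed index visit makes the comparison free of bias. Under the planned schedules, first crossing still gives an effect size of about 0.96 from monthly versus quarterly sampling alone, which is a separate matter.

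**What to change.** For the analysis only:

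- In Section 8.3, define the index visit as the first visit whose recorded values meet the protocol's trigger, derived by program identically in both arms. This matches the hypothesis in Section 1.1 and the simulation in Section 8.2.
- Reconcile the MIP criterion between Sections 2.1 and 3.2 and Section 7.2.2, so that there is one trigger to program. Which statement is right is a clinical matter for the investigators.
- State how dyspnea is read from data already collected in both arms, for example the monthly MDRS-D. Alternatively, use the recorded FVC crossing as the primary index. If the MDRS-D is used, clarify how it is completed at tele-visits, since Section 7.2.2 has the therapist administer the survey there but also has surveys after month 0 completed online.
- Report the actual recommendation date, and the values at that date, as secondary.

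The clinical recommendation process is unchanged, and no new visit or assessor is needed. The cost is a few lines of plan text and code. The index may differ from the clinical recommendation in a few patients, and the therapist still decides which maneuvers are valid.

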### **7.3 Duration of Participation**

Part 1: The study procedures, including screening, consent, assessment, and survey, are expected to take 45 minutes. Administration of the simulated PFT with patient participants will be performed on the day of a scheduled clinic visit.

Part 2: The participant team will be enrolled for approximately one year. During this time, participants will engage in approximately five standard PFT assessments as part of normal clinical activities, requiring no additional time commitment. All participants will complete monthly surveys which will take 15 minutes each. Those in the experimental arm will also complete eight rPFTs, each taking 30 minutes. Control participants will be required to devote approximately 3.25 hours over the course of the study, and those in the experimental arm will devote approximately 7.25 hours.

## **8.0 Subject Numbers and Statistical Plan**

### **8.1 Number of Subjects**

Approximately (but no more than) 103. We will enroll 40 patient/caregiver teams for Part 1 and 40 patient/caregiver teams for Part 2. Participants in the two studies may overlap. Up to 20 practice control participants may be recruited for Part 1. Up to three respiratory therapists will also be recruited for these studies.

### **8.2 Sample size determination**

Our sample size is predetermined based on our subjective ability to recruit patients within the time frame of the study. Power analysis was based on studies of FVC decline. Lo Coco et al., [LoCoco2006], showed that 50% of study participants dropped below 50% predicted FVC in one year. Given that our exclusion criteria for Part 2 will reject many of the 37% of individuals in their study who were "slow progressors," we estimate that 75% of patients enrolled in our study will meet the respiratory criteria to recommend NIV. This results in a sample size per arm of n=15, which provides 80% power to detect a difference in mean outcome between the two groups if the effect size is found to be 0.95.

Assuming a monthly change in FVC of  $3.5 \pm 3.4\%$  found by Schiffman et al. [Schiffman1993], we conducted 10,000 Monte-Carlo simulations of 40 participants declining at this rate for 12 months. Half were sampled once every three months, and half were sampled every month.  $80.6 \pm 6.3\%$  of simulated participants met the requirements for NIV recommendation, in roughly equal proportions across groups. The average FVC at recommendation was 47.0% predicted in the experimental group, and 43.4% predicted in the control group. The effect size of the difference in FVC between groups was  $.964 \pm .343$ . Similarly, the two measures of QoL obtained at NIV recommendation are powered with an 80% chance to detect improvement of quality of life in the experimental group if the effect size is also found to be 0.95. This corresponds to a mean score difference of 1.52 on the SAQLI, assuming a standard deviation of 1.6 [Flemons1998]. Although there is no published data on the standard deviation of MDRS-D scores, the range and format of questions is similar enough to estimate a comparable difference between groups is needed.

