### **3.3 Early Withdrawal of Subjects**

#### **3.3.1 Criteria for removal from study**

Participants may voluntarily withdraw from the study at any time. The research team may also terminate the study if the participant team exhibits one or more of the exclusion criteria during the course of the study.

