#### **3.3.2 Follow-up for withdrawn subjects**

The research team will follow up with withdrawn subjects at their home to collect the research equipment. If the participant team agrees, they will be given the endpoint assessment to document their reason for withdrawal. There will be no follow-up. The withdrawn subjects may be replaced by another patient and caregiver from the recruitment waitlist.

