Following the initial visit (month 0), participants will undergo randomization. Those randomized to the experimental group will be shipped an rPFT kit and scheduled for monthly telemedicine appointments between clinic visits. On the dates of the telemedicine appointments, the respiratory therapist administers the study survey and conducts an rPFT from clinic with the patient in their home. This is repeated for the 2nd month. On the 3rd month, the participant dyad is seen by the therapist during their normal clinic visit. This pattern is repeated until the 5th clinical appointment (including the visit at month 0), resulting in 5 in-person assessments and 8 intermediate tele-assessments over the course of approximately 12 months. The control arm will receive standard assessments during regular ALS clinic appointments (Table 1), and be required to complete a study survey each month. Study procedures will be followed until the study endpoint at month 12, even if NIV is initiated during this period. The treating neurologist will make the decision to end the protocol early if the patient is unable to perform the procedures. The patient can also opt to end the study at any time.

The study survey is administered once a month for participants in both study arms and consists of four parts. The initial survey administered at month 0 will be completed with a researcher present. The remaining surveys will be completed online. If it coincides with administration of a PFT or rPFT, it will be administered first. It is designed to measure the impact of daytime breathlessness and sleepiness on QoL and consists of the following components.

- 1) Sleep Apnea Quality of Life Index (SAQLI) - part D [Flemons1998]. It is designed to assess quality of life pertaining to sleep disturbances, as well as the impact of treatment on QoL. It has been used as a sensitive measure of health-related QoL in ALS [Bourke2006, Jackson2001, Bourke2003].
- 2) Motor Neurone Disease Dsypnoea Rating Scale (MDRS) - subscale D [Dorman2007]. Dorman et al. described an ALS-specific assessment, the Motor Neurone Disease Dsypnoea Rating Scale (MDRS), as one with high construct validity and responsiveness. The dyspnea subscale (MDRS-D) of this tool has patients choose which activities of daily living they have experienced shortness of breath in the past two weeks and how severe the episode was [Dougan2000].

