### **16.2 Feasibility of recruiting the required number of subjects**

We anticipate high interest in Part 1 due to the short time commitment and participation during a single clinical visit. We anticipate no issues recruiting 40 individuals for this study. The resource and timing limitations of Part 2 will make enrollment more challenging. Forty participants, half of which will be randomized to the experimental group, will take place in this year-long study. We anticipate the participation of two respiratory therapists to aid with rPFT administration.

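### The 80% power stated for Part 2 makes no allowance for patients lost before an NIV recommendation, so it holds only with complete retention or full replacement

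*Combined protocol and SAP*

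**What the plan says.** Part 2 is to enrol "40 patient/caregiver teams for Part 2" (8.1), split equally: "Forty participants, half of which will be randomized to the experimental group" (16.2). That is 20 per arm.

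Section 8.2 says that N was set by what the team could recruit. From published rates of FVC decline and the share of slow progressors, it then reasons: "we estimate that 75% of patients enrolled in our study will meet the respiratory criteria to recommend NIV". The next step is "This results in a sample size per arm of n=15, which provides 80% power" at effect size 0.95. The same effect size is carried to the quality-of-life outcomes, where it is given as 1.52 SAQLI points at an SD of 1.6. The simulation in 8.2, as described, has 40 participants declining for 12 months, of whom 80.6% meet the NIV criteria. It mentions no losses.

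Other sections provide for loss:
- 3.3.1: "Participants may voluntarily withdraw from the study at any time", and the team may also remove participants.
- 7.2.2: "The treating neurologist will make the decision to end the protocol early if the patient is unable to perform the procedures".
- 3.3.2: withdrawn participants are not followed up, but "The withdrawn subjects may be replaced by another patient and caregiver from the recruitment waitlist".

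Section 8.3 compares respiratory parameters and quality of life at the point of NIV recommendation, using the Wilcoxon-Mann-Whitney test. Neither alpha nor sidedness is stated.

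**The concern.** A patient who dies, withdraws or is stopped before an NIV recommendation contributes nothing to the comparison in 8.3. The evaluable number per arm is therefore 20 × (share meeting criteria) × (share still in the study when they would meet them). Section 8.2 includes the second factor and leaves out the third, which amounts to setting it to 1. The 75% is derived from how fast FVC falls, so it describes disease course and cannot be read as already net of loss.

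In a year-long ALS study that has survival among its own hypotheses, complete retention up to recommendation is a strong assumption to leave unstated. At stake is how the result will be read: a null finding would be taken as coming from a trial with 80% power at effect size 0.95, when the trial may have had less.

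**Working it through.** **Inputs.** 20 per arm (8.1, 16.2); share meeting criteria p = 0.75, or 0.806 from the simulation (8.2); effect size d = 0.95 (8.2); SAQLI SD 1.6 (8.2). Assumptions, because the documents are silent: alpha 5%, tried one- and two-sided, and a proportion L lost before recommendation and not replaced, from 0% to 30%.

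**Step 1: the plan's n.** 0.75 × 20 = 15.0, exactly the printed figure, with no loss term.

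**Step 2: the plan's power.** For a t-test with n per arm, the noncentrality is d × √(n/2) on 2n − 2 degrees of freedom. At n = 15 this is 0.95 × √7.5 = 2.60 on 28 df.
- One-sided 5%: 81.4% (t-test); 79.7% (rank-sum, by scaling n by 3/π).
- Two-sided 5%: 70.9% (t-test); 68.8% (rank-sum).

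Of these, only one-sided 5% (equivalently two-sided 10%) reproduces the printed 80%.

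**Step 3: add loss.** The expected evaluable number per arm is 20 × p × (1 − L). Because the number reaching recommendation is random, power is averaged over independent Binomial(20, p(1 − L)) counts in the two arms. This is why the zero-loss figure is 80.8% and not 81.4%.

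| Loss before recommendation, L | Evaluable per arm (p = 0.75) | Power, t-test, one-sided 5% | Same, p = 0.806 |
|---|---|---|---|
| 0% | 15.0 | 80.8% | 83.5% |
| 5% | 14.25 | 78.8% | 81.6% |
| 10% | 13.5 | 76.7% | 79.6% |
| 20% | 12.0 | 71.8% | 74.8% |
| 30% | 10.5 | 66.1% | 69.2% |

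At p = 0.75, the rank-sum version of the same average is lower by nearly 2 points: 79.2%, 74.9% and 70.0% at 0%, 10% and 20% loss. At two-sided 5%, the t-test gives 70.3%, 65.1% and 59.3% at the same losses.

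**Step 4: detectable difference.** Holding power at 80% (t-test, one-sided 5%, n fixed at its expected value), the effect size needed is 0.93 at n = 15, and 0.98, 1.05 and 1.13 at 10%, 20% and 30% loss. Multiplied by the SD of 1.6, the last three are about 1.57, 1.68 and 1.80 SAQLI points, against the printed 1.52.

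**Step 5: slack from the simulated share.** 0.806 × 20 = 16.1 per arm. This stays at 15 or more while L ≤ 1 − 15/16.12 = 6.9%.

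**The case against.** The case for leaving 8.2 alone has four parts.

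*Losses can be replaced.* Section 3.3.2 allows it and sits under the general heading on early withdrawal, so it may reach beyond voluntary withdrawals. A reader might infer that the ceiling in 8.1, "Approximately (but no more than) 103", rules replacement out, because 40 + 40 + 20 + 3 = 103. The documents do not support that: Part 1 and Part 2 participants may overlap, practice controls and therapists are stated as maxima, and 16.2 expects two therapists. What stands is that replacement is optional, deaths are not named, and 8.2 does not rely on it.

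*Small losses hardly matter.* This is right. At 5% loss the cost is about 2 points, and the simulated 80.6% share absorbs about 7% before the expected number falls below 15. It is therefore too strong to say that any realistic loss leaves fewer than 15 evaluable.

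*Only loss before recommendation counts.* This is also right. Putting a full 12-month loss rate into the formula would overstate the effect. As an illustration, in a rerun of the FVC decline with an assumed starting value of 82% predicted (not in the documents) and exponential loss of 20% per year, evaluable numbers fell from 16.1 to 13.5 in the control arm and from 16.3 to 13.9 in the experimental arm. That is a loss of 1 − 13.5/16.1 = 16% and 1 − 13.9/16.3 = 15%, not 20%.

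*Nothing is miscalculated, and N was fixed by feasibility.* 0.75 × 20 is 15, and 8.2 is open about recruitment capacity and conditions its power on the effect size. The fault is an unstated assumption, not an arithmetic error. But 8.2 still prints a power figure, and that figure should carry its condition.

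**Conclusion.** The point holds in a limited form. The printed 80% is reproducible, but only at one-sided 5% and only if every patient is retained to recommendation or fully replaced. Any loss before recommendation that is not replaced lowers both the evaluable number and the power: by about 2 points at 5% loss, 4 at 10%, 9 at 20% and 15 at 30%, measured from 80.8%.

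The sizes rest on assumptions: the loss rates are a range because the documents give none, loss is taken as independent of progression, and alpha and sidedness are inferred from the printed 80%. That last gap is at least as large. At two-sided 5%, power is about 70% before any loss, roughly what 20% loss costs under the one-sided reading. Restating power for attrition alone would leave it hidden.

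A reader might also infer that the trial must enrol more patients. The documents do not support that demand, because N was set by recruitment capacity. What needs correcting is the statement of power.

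**What to change.** In 8.2:
1. State the expected loss before NIV recommendation, with its source (for example, the clinic's own records of deaths and discontinuations before that point). Do not use the full 12-month loss.
2. Say how deaths, early stops and replacements count toward the 15 per arm, including whether patients who die or are stopped may be replaced.
3. Restate power, or the detectable effect size and SAQLI difference, for the planned rank-sum test over a range of losses such as 0% to 30%.
4. Give alpha and sidedness beside every power figure.

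This is a wording change plus a short recalculation. Enrolment, procedures and endpoints stay as they are. The only cost is a less favourable stated power.
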